### 5.3. Data sources that will be used to collect data about subjects:

**Aim 1:** Data will be derived from qualitative participant feedback (interviews, participatory design sessions and usability feedback). The source records that will be used to collect data from participants (e.g. question guides) are attached to the Click Smartform. The qualitative question guides will change iteratively based on feedback from participants, but themes explored will remain the same, consistent with best practices for qualitative data collection. Please note that all materials will be translated to Spanish and uploaded as an IRB modification prior to recruitment of Spanish speaking participants.

**Aims 2 and 3:** Parents will complete surveys at three time-points: (1) at initial ED visit before discharge, (2) one day post-visit, and (3) approximately two-weeks post-visit. The first survey will be administered over the phone by the study team member. Surveys will be translated into Spanish using a certified translation service and the research team member involved in parent data collection will be certified to use Spanish or use a professional interpreter. Participating parents will be contacted one day post-visit and two-weeks post-visit to complete the follow up survey by telephone (call or text linking to a survey hosted on REDCap), or by email (linking to a survey hosted on REDCap). Subsequently, a purposively selected subset of twelve parents will be invited to participate in a one-on-one qualitative interview about their experiences with the education toolkit; additional parents may be recruited if necessary to reach thematic saturation. Please note that all materials will be translated to Spanish and uploaded as an IRB modification prior to recruitment of Spanish speaking participants.

**Aim 4:** (1) Cognitive interviews: Data will be derived from qualitative participant feedback (e.g., cognitive interviews). The source records that will be used to collect data from participants (e.g., question guides) are attached to the Click Smartform. (2) Online surveys: Data will be collected through an online surveys, built in REDCap with the survey link posted on MTurk.

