randomized to either the education toolkit intervention condition or treatment-as-usual control condition in a 2:1 ratio. For participants in the control group (Aim 2 and those randomized to control group in Aim 3), there will be no change to the nature of provider communication with families about closed head injury/concussion. Data will be collected about the experience that family's have seeking care in the ED for their child's closed head injury. For both Aims 2 and 3, survey data will be collected from parents at three time points: at initial ED visit before discharge, one day post-visit, and at 2-week follow-up. As part of parent data collection for Aims 2 and 3, all parents will complete the 3-item Brief Health Literacy Screen at the first time point of survey data collection. Please see timeline (uploaded in "Other Attachments" for more information regarding the timing of Aims 2 and 3.

For Aim 3 participants randomized to the intervention group, the parent education toolkit finalized in Aim 1 will be delivered by the study team. Based on feedback from qualitative interviews in Aim 1, the toolkit will consist of brief education from a member of the ED study team at enrollment, followed by asynchronous phone-based follow-up (audio/ voice and/or text). Parents will receive automated daily educational messages related to how they can provide recovery support to their children during the 2-week study period. Automated messages will be delivered via Twilio, by turning on the "initiate survey as SMS conversation" feature in REDCap. Parents will also receive reminders to schedule a follow-up appointment, with an option to receive tailored support from research staff to help with scheduling. A more detailed description and content of each toolkit component can be found in "Aim 3 Parent Education Toolkit Content" uploaded in "Other Attachments".

All patient materials will be available in both English and Spanish. Certified translations will be uploaded prior to use.

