### 5.4. Data to be collected, including long-term follow-up data:

**Aim 1:** The goal of the parent interview will be to (1) explore their experiences with communication in the ED following their child's concussion and (2) provide critical feedback on the content and design of the CDC ACE Care Plan. The Cultural Treatment Adaptation Framework, will provide the foundation for the open-ended question guide for parents, with questions about the handout focusing on: (1) language and semantics, (2) use of culturally relevant examples, and 3) preferences for material delivery. The goal of the healthcare provider interviews will be to review the CDC ACE Care Plan handout and the RED Toolkit, and provide feedback about (1) barriers and facilitators to implementation in the ED and (2) the type of support (e.g., materials, training) that they believe would be helpful for implementation. CFIR^24 will provide the foundation for the open-ended question guide for healthcare providers, with a focus on individual characteristics (e.g., provider knowledge and self-efficacy), implementation toolkit characteristics, and aspects of the inner setting (e.g., time pressures in the busy ED, compatibility with existing communication networks and tools such as the EHR system) that may constrain implementation success.

**Aims 2 and 3:** Survey data will be collected from up to 200 parents at three time points: at initial ED visit before discharge, one day post-visit, and at 2-week follow-up. **Primary outcome.** Our primary outcome will be parenting behaviors at 2 week follow-up (emotional support and instrumental support). **Secondary outcomes.** Parent surveys at initial ED visit before discharge, one day post-visit, and two-weeks post visit will assess parent cognitions related to concussion management and proximal cognitions (concussion management knowledge and self-efficacy), parental anxiety related to concussion management, youth outcomes (health-related quality of life, post-concussion symptoms), the nature of provider-parent communication in the ED (e.g., did the parent have an opportunity to ask questions?), and additional

covariates (demographics and environmental conditions). In Aim 3 only, the parent surveys at 2 weeks post-visit will also include questions about their experiences with receiving the education toolkit.

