#### **Aims 2 and 3:**

Parents: Initial research activities will occur over the phone while the participants are in or near the SCH ED and Urgent Care. Follow-up (at one day post-visit and approximately 2 weeks post-visit) will occur remotely (by telephone—text, or phone call—or email, depending on the participant's preferences ). Before any research procedures begin, the study team member will explain that participants may choose

to skip any questions they do not want to answer and they may discontinue the research study at any time. Research procedures will be conducted in English or Spanish, depending on the preference of the participant. All information will be stored on secure servers at the Seattle Children's Research Institute overseen by the Principal Investigators. Study staff will have access to this data as needed for participant contact purposes.

. Subsequent qualitative interviews with parents will be audio-recorded and transcribed verbatim, with all data stored on secure servers at the Seattle Children's Research Institute overseen by the Principal Investigators.

**Aim 4:** (1) Cognitive interviews: All research activities will occur in person in or near the SCH ED and Urgent Care. Before any research procedures begin, the Research Assistant will explain that participants may choose to skip any questions they do not want to answer and they may discontinue the research study at any time. All information will be stored on secure servers at the Seattle Children's Research Institute overseen by the Principal Investigators. No personal health information about participants will be collected; (2) Online surveys: Prior to accessing the surveys, participants will receive information about the purpose of the study (validating a survey tool to measure concussion related behaviors, knowledge, and self-efficacy) and the eligibility criteria for the study. They will be informed that participation is voluntary and anonymous. No personal health information about participants will be collected.

**19.3. Sources of subjects:**

Chart screening or provider referral, as described in section 19.1

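### The primary outcome is self-reported by coached, unblinded parents, and nothing stops the person who calls for the two-week survey from being their educator or knowing their arm

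*Combined protocol and SAP*

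**What the plan says.** **Outcome and source.** Section 5.4 makes parenting behaviours (emotional and instrumental support) at two weeks the primary outcome. Section 5.3 gives the source: "Parents will complete surveys at three time-points". No objective or third-party measure of these behaviours is described.

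**Mode.** "The first survey will be administered over the phone by the study team member", according to section 5.3. For the later surveys, parents are contacted "to complete the follow up survey by telephone (call or text linking to a survey hosted on REDCap), or by email". Section 19.2 describes remote follow-up "by telephone—text, or phone call—or email, depending on the participant's preferences".

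**Intervention contact.** Section 5.2 states that "the parent education toolkit finalized in Aim 1 will be delivered by the study team". An ED study team member gives brief education at enrolment. Automated daily messages on supporting recovery follow for two weeks, and research staff can help with scheduling. Controls have no change in provider communication, and no attention control is described.

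**Toolkit questions.** For Aim 3, section 5.4 adds that "the parent surveys at 2 weeks post-visit will also include questions about their experiences with receiving the education toolkit".

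**What is absent.** No section mentions blinding, says who places the two-week calls, separates callers from educators, sets the order of the items, or provides for recording mode. The analysis plan in 14.1 names neither mode nor caller. Quality control in 14.2 covers staff training and review of recorded interviews.

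**The concern.** Only intervention parents are taught the behaviours that the primary items ask about, so only they have been told what a good answer looks like. If the question then comes by telephone from someone they associate with the teaching, or who knows they were taught, they have a reason to over-report that controls lack. A caller who knows the arm may also probe or record differently.

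Such a bias pushes in one direction. Randomisation does not remove it, because it arises after allocation. The adjustment covariates named in 14.1 (child age, sex, baseline symptoms or severity) do not address it. A larger sample does not dilute it, and only makes it more likely to reach significance. What is at stake is whether a positive result reflects what parents did or what they said to the study team.

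**Working it through.** **The plan's own figure.** Section 10.4 states at least 98% power for a 20-point difference with 200 per group, 10% attrition and alpha 0.05. With 200 × 0.9 = 180 per group and a two-sided test, power is 99.8% for 10% vs 30%, 98.7% for 20% vs 40%, 97.5% for 30% vs 50% and 96.9% for 40% vs 60%. The statement reproduces to within about one point. It concerns reach components in Aim 2 vs Aim 3, not the primary outcome by randomised arm, and power says nothing about measurement bias.

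**Inputs to the illustration.**
- From the documents: Aim 3 of 200 parents, 10% attrition, 2:1 allocation, alpha 0.05. This gives 180 parents, or 120 intervention and 60 control.
- Assumed, because the documents give no values: a two-sided test; a true rate *p* of 30%, 50% or 70% in both arms; the size of the reporting shift *b*; and the share answering by call.

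**Formula.** For one behaviour item, the normal approximation to the chi-squared test with control rate *p* and reported intervention rate *p* + *b* is

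P(reject) = Φ[(*b* − 1.96 *s*₀)/*s*₁] + Φ[(−*b* − 1.96 *s*₀)/*s*₁],

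where *s*₀ is the pooled and *s*₁ the unpooled standard error.

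*Arm-wide shift of 5 points, p = 50%.* The pooled rate is (60 × 0.50 + 120 × 0.55)/180 = 0.533. Then *s*₀ = √(0.533 × 0.467 × (1/60 + 1/120)) = 0.0789, and *s*₁ = √(0.25/60 + 0.2475/120) = 0.0789. The two terms are Φ(−1.33) = 0.092 and Φ(−2.59) = 0.005, giving 0.097.

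*Ten points among callers only.* If 30% of intervention parents answer by call, the shift over the arm is 0.30 × 10 = 3 points. The pooled rate is 0.52, and *s*₀ and *s*₁ are both 0.0790. The terms are Φ(−1.58) = 0.057 and Φ(−2.34) = 0.010, giving 0.067.

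| Shift over the whole intervention arm | p = 30% | p = 50% | p = 70% |
|---|---|---|---|
| 0 points | 5.0% | 5.0% | 5.0% |
| 3 points | 6.7% | 6.7% | 7.3% |
| 5 points | 9.9% | 9.7% | 11.5% |
| 10 points | 25.3% | 24.8% | 32.8% |

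If Aim 2 controls are pooled with Aim 3 controls (180 + 60 = 240 vs 120, *p* = 50%), the rates are 8.3%, 14.5% and 43.3% for 3, 5 and 10 points.

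**Mode on its own.** If calls raise reporting by *m* points in both arms alike, the bias is *m* × (call share in intervention − call share in control). With *m* = 20 and equal shares it is zero. With 20 points more calls in the intervention arm it is +4 points; with 20 points fewer it is −4 points. Intervention parents are already in text contact with the study, which would if anything suggest fewer calls in that arm, so this component could shrink the difference.

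**The case against.** **The documents do not say that the educator calls.** This stands. A reader might infer that the same people teach, call and know the arm. Section 5.2 assigns the education to an ED study team member and the scheduling help to research staff, and sends the messages automatically. Section 25.2 lists a project coordinator with time for data collection. Overlap is possible, not shown. The defect is that nothing excludes it.

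**Mode differences do not clearly favour the intervention.** This also stands. A reader might infer that unequal modes enlarge the effect. As the working shows, the sign depends on call shares that nobody has stated.

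**A large arm-wide shift overstates a mechanism that works through calls.** This stands. The 25% for a 10-point shift should not be read as the likely inflation, since it requires every intervention parent to over-report, including those answering by link.

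**Item order cannot be judged, and parents know what they received.** This stands in part. The survey is an attachment and its order is not visible. Parents need no cue, but a caller who was otherwise masked would learn the arm from the toolkit questions.

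**Self-report is inherent and flexible mode has a purpose.** This is true. Section 22.2.2 notes, for Aim 1 consent, that electronic requirements limit participation by families with fewer resources. Language coverage may also limit who can call Spanish-speaking families. These are reasons to keep calls available, not to leave the caller unmasked.

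**Conclusion.** The concern holds as an avoidable risk of directional reporting bias in the primary outcome. Parents' lack of blinding is an inference, but a safe one: staff education and daily messages set against unchanged communication cannot be concealed from the recipient.

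The documents give nothing from which to derive the size of the bias. For the randomised comparison of 120 vs 60 with 50% in both arms, the false-positive rate is about 10% under an arm-wide 5-point shift, and about 7% if 10 points apply only to an assumed 30% answering by call. The cover note reports a smaller sample than planned. At an assumed 60 vs 30, a 5-point shift gives about 7%, but the bias in the estimate is still 5 points.

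The documents do not support saying that the educator makes the call, that mode differences inflate the effect, or that the bias is of any particular size. Masking the caller would also not remove the whole problem, because coached parents may over-report in self-completed surveys too.

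**What to change.** In section 5.3, for both arms:

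- Have two-week calls made, with a fixed script, by an existing team member who did not enrol or educate that family, with the allocation field hidden in REDCap. Where language coverage prevents this, record it.
- Put the primary behaviour items first and the toolkit-experience items last, on a separate page.
- Offer the same modes in the same order: the self-completed link first, with a call freely available on request or after non-response.
- Record mode and caller for each survey, and report mode by arm.

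In section 14.1, state that any analysis by mode is descriptive or exploratory. Mode is chosen after randomisation and may track literacy and language. Comparing arms only among self-completed surveys could therefore introduce selection bias and drop low-literacy parents, the group the study is meant to serve.

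The cost is some REDCap settings, a call-assignment rule within the present team and one table. The downside is small: less flexibility in who calls. The steps must be in place before two-week data are collected, because caller and item-order effects cannot be undone and an unrecorded mode cannot be reported. For surveys already completed, report whatever was kept on mode and caller, and state the limitation.

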### 5.4. Data to be collected, including long-term follow-up data:

**Aim 1:** The goal of the parent interview will be to (1) explore their experiences with communication in the ED following their child's concussion and (2) provide critical feedback on the content and design of the CDC ACE Care Plan. The Cultural Treatment Adaptation Framework, will provide the foundation for the open-ended question guide for parents, with questions about the handout focusing on: (1) language and semantics, (2) use of culturally relevant examples, and 3) preferences for material delivery. The goal of the healthcare provider interviews will be to review the CDC ACE Care Plan handout and the RED Toolkit, and provide feedback about (1) barriers and facilitators to implementation in the ED and (2) the type of support (e.g., materials, training) that they believe would be helpful for implementation. CFIR^24 will provide the foundation for the open-ended question guide for healthcare providers, with a focus on individual characteristics (e.g., provider knowledge and self-efficacy), implementation toolkit characteristics, and aspects of the inner setting (e.g., time pressures in the busy ED, compatibility with existing communication networks and tools such as the EHR system) that may constrain implementation success.

**Aims 2 and 3:** Survey data will be collected from up to 200 parents at three time points: at initial ED visit before discharge, one day post-visit, and at 2-week follow-up. **Primary outcome.** Our primary outcome will be parenting behaviors at 2 week follow-up (emotional support and instrumental support). **Secondary outcomes.** Parent surveys at initial ED visit before discharge, one day post-visit, and two-weeks post visit will assess parent cognitions related to concussion management and proximal cognitions (concussion management knowledge and self-efficacy), parental anxiety related to concussion management, youth outcomes (health-related quality of life, post-concussion symptoms), the nature of provider-parent communication in the ED (e.g., did the parent have an opportunity to ask questions?), and additional

covariates (demographics and environmental conditions). In Aim 3 only, the parent surveys at 2 weeks post-visit will also include questions about their experiences with receiving the education toolkit.

**Parent Interviews** (Aim 3 only): Based on parents' responses to their experiences with the education toolkit, a purposive recruitment strategy will be used to invite by email 12 parents to participate in one-on-one qualitative interviews. Interview content will be based on the Consolidated Framework for Implementation Research and Communication Accommodation Theory, assessing their experiences implementing content of the intervention, and their affective experience engaging with educators. Following best practice guidance for eliciting qualitative data about implementation barriers and facilitators and communication experiences, the question guide will remain open ended so that interviewers can explore other themes raised by participants.

**Aim 4:** (1) Cognitive interviews: The goal of the cognitive interview will be to assess understanding of survey questions and receive feedback on survey content. Research assistants will talk through questions with parents and identify 1) if question wording is confusing or challenging in any way, and 2) if questions could be asked in a way that is easier to understand. (2) Online surveys: The surveys will primarily assess parent behaviors, knowledge, and self-efficacy related to concussion management in order to validate our survey tool. Additional covariates (such as demographic information, previously diagnosed concussion) will also be collected for the purpose of ensuring the survey tool is valid and reliable for the general population. Survey questions will come from a bank of potential questions, which can be found in the support document "Aim 2 Parent Survey Questions".

## 6. Data and Biospecimen Banking

6.1. Complete list of the data and/or biospecimens to be included in the bank:

N/A

6.2. Location of data and/or biospecimen storage:

N/A

6.3. List of those with direct access to data and/or biospecimens in the bank:

N/A

6.4. Length of time data and/or biospecimens will be stored in the bank:

N/A

6.5. Procedures for protecting the confidentiality and privacy of the subjects from whom the data and/or biospecimens were collected:

N/A

6.6. How the data and/or biospecimens will be made available for future use:

N/A

6.6.1. Who can request data and/or biospecimens from the bank:

N/A

6.6.2. Format in which data and/or biospecimens will be provided:

N/A

6.6.3. Process for investigators to request data and/or biospecimens:

N/A

**6.6.4.** Restrictions on future use:

N/A

**6.6.5.** Plan for providing data results from banked data/biospecimens:

N/A

**7. Sharing of Results**

**7.1.** Plan to share results with subjects/others:

Aggregate data will be shared with members of the research team and disseminated via peer reviewed publication. No personal identifiers will be shared.

**8. Study Timelines**

**8.1.** Duration of an individual subject's participation in the study:

**Note:** Aims are not numbered in chronological order, however they will be listed below in the order they will be collected.

**Aim 4:** (1) Cognitive interview: For each parent, the endpoint will be the conclusion of the cognitive interview; (2) Online surveys: For each participant, the endpoint will be the conclusion of the online survey.

**Aim 1:** For each participant, the endpoint will be the conclusion of the interview. For healthcare providers participation will conclude following completion of a survey and/or qualitative interview.

**Aims 2 and 3:** In the first data collection cohort (Aim 2), all participants will be assigned to the education-as-usual control condition. In the second cohort (Aim 3), participants will be randomized to either the education toolkit intervention condition or treatment-as-usual control condition in a 2:1 ratio. For each parent in the control group and for most parents in the intervention group, participation will conclude after completing the two-week post-discharge survey. For a subset of parents in the intervention group who agree to participate in a follow-up interview, participation will conclude at the end of a qualitative interview following the data collection period.

**8.2.** Duration anticipated to enroll all study subjects:

**Aim 4:** 1 month

**Aim 2:** 5 months (potentially up to 9 months)

**Aim 1:** 12 months (potentially up to 18 months)

**Aim 3:** 5 months (potentially up to 9 months)

**8.3.** Estimated date for the investigators to complete this study:

Primary analyses will be completed about 2 years after the start of the study

